10.3.4.1 Study Feedback Questionnaire

At Visit 4, a study feedback questionnaire will be completed. This will collect participants' feedback on the feasibility and acceptability of the study procedures. An email containing the link to the study feedback questionnaire (as well as the contact questionnaire) will be sent, which will be notified to the participant via a text reminder. This could also be completed in person with the study team using the hand held device provided, or a paper copy of the feedback questionnaire can be posted to the participant's home address.

10.3.4.2. Screening Newborn for cCMV

Although the vertical transmission rate for non-primary maternal CMV infection (as all participants are CMV seropositive) is very low at around 2% [Liesnard 2000; Revello 2002], all participants entering into the cCHIPS study will be offered the opportunity for their newborn to have cCMV screening where a saliva swab of the newborn will be collected by the study team. This will be done within the first week of the newborn's life, to ensure that if the newborn was diagnosed with cCMV and meets the criteria for treatment, this can be done in a timely way, as the current guidelines recommend treatment to begin within the first month of life. The decision to offer to screen the participants' newborns for cCMV was made following a discussion with our PPI group.

A positive CMV salivary swab result will be communicated to the participants by phone by a clinically qualified member of the research team and arrangements will be made for appropriate clinical follow up. This will involve referral to the paediatric infectious diseases team, according to established clinical pathways. Responsibility for the clinical care of the newborn, whether established as having cCMV infection or not, will remain with the clinical team

9.4 Summary flow chart of study assessment

*If consent obtained

9.5 Process Evaluation

Up to 20 participating mothers will be asked to take part in a process evaluation at the end of the study. Consent for this will be included in the consent form at the start of the study. This will be done by phone, skype or face to face interviews at the convenience of the participants. Interviews will be recorded. The recording will start after introductions have been done and will only contain first names. These recordings will be stored securely on NHS or University computers before being transcribed. After transcription the audio files will be destroyed. Interviews will be a maximum of 40 minutes long. Interviews will be performed until data saturation is reached, that is until additional interviews will not provide new information over and above that already obtained. The interviews will explore in depth their experiences during the study participation. They will explore optimal ways for information to be shared in future studies.

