8.4 Discontinuation/withdrawal of participants and stopping rules

In consenting to the study, participants are consenting to study interventions, study follow up and data collection. However, an individual participant may stop study participation early or be stopped early for any one of the following reasons:

Any change in participant's situation that in the investigator's opinion justifies the discontinuation of study participation.

As participation in the study is entirely voluntary, the participant may choose to discontinue participation at any time without penalties or loss of benefits to which they may be entitled. Although not obliged to give a reason for discontinuing their participation a reasonable effort should be made to establish this reason, whilst remaining fully respectful of the participant's rights.

If a participant chooses to withdraw from the study, we will ask if they would be willing to complete the study feedback questionnaire at the time of withdrawal. If no follow up is possible data that has already been collected should be kept and analysed according to the ITT principle for all participants who stop follow up early.

As this is a feasibility study, once a participant has been recruited into the study and completed the first study visit (Visit 1), if a participant chooses to withdraw after this point due to non-compliance to part of the study procedures (not all), for instance non-compliance to vaginal secretion sampling or venous blood taking, we will ask if the participant is willing to continue participating in the study and complete the rest of the study procedures that the participant is willing to comply with.

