14.2.2 Secondary endpoints

- The percentage of subjects with detectable CMV virus in saliva (measured via quantitative PCR) at individual study visits and cumulatively
- The percentage of subjects with detectable CMV virus in urine (measured via quantitative PCR) at individual study visits and cumulatively

- The percentage of subjects with detectable CMV virus in the vaginal secretions (measured via quantitative PCR) at individual study visits and cumulatively
- The quantity of CMV virus in saliva (measured via quantitative PCR) in the subjects at individual study visits cumulatively
- The quantity of CMV virus in urine (measured via quantitative PCR) in the subjects at individual study visits and cumulatively
- The quantity of CMV virus in vaginal secretions (measured via quantitative PCR) in the subjects at individual study visits and cumulatively
- Risk factors associated with CMV shedding in the subjects
- Assessment of the acceptability of the study procedures to participating pregnant women
- Proportion of subjects approached who are willing to participate in the study
- Proportion of subjects completing the study

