13.4.3 Secondary endpoint analysis

For each sample type (saliva, urine, vaginal secretions), the percentage of participating women with detectable CMV DNA as measured by quantitative PCR, will be calculated for each study visit (Visit 1, Visit 2, Visit 3, Visit 4), and cumulatively, with 95% CIs.

For each study visit (Visit 1, Visit 2, Visit 3, Visit 4), the percentage of participating women with detectable CMV DNA as measured by PCR, will be calculated for each sample type (saliva, urine, vaginal secretions), and cumulatively, with 95% CIs

CMV shedding will also be assessed quantitatively, as measured by quantitative PCR on the amount of CMV DNA detected, in each sample type and at each study visit, separately and cumulatively, with 95% CIs.

The distributions of sample type, study visit number, detectable shedding and quantity of shedding will be summarised graphically and described using means and medians, as appropriate.

Factors associated with CMV shedding as a binary outcome (detectable shedding versus no detectable shedding) will be investigated using multivariable mixed effects models. Potential risk factors will be those assessed using the study sociodemographic questionnaire at Visit 1 and risk factor questionnaires at all visits (these variables may be time-varying) – these will include ethnicity, age, number of children, parental occupation, age of child(ren), and type of handling with child(ren)'s urine and saliva.

Acceptability of the study design and procedures will be analysed descriptively, for example by calculating mean scores derived from satisfaction scales. We will also investigate factors associated with satisfaction, defined as a binary variable, using logistic regression. We will summarise free text comments made through the feedback questionnaire.

The percentage of eligible women who consent to participate, and the percentage of participants who complete the study (provide urine, saliva and vaginal secretion samples and questionnaire data at all four study visits, with or without blood and newborn saliva samples), will be calculated.

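### Acceptability is at risk of upward bias: feedback from women who leave is only partly sought, is not reported by completion status, and the interviews do not deliberately include them

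*Combined protocol and SAP*

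**What the plan says.** Section 14.2.2 lists as a secondary endpoint "Assessment of the acceptability of the study procedures to participating pregnant women". No target, threshold or precision is attached to it.

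**Collection.** Section 10.3.4.1 states: "At Visit 4, a study feedback questionnaire will be completed". The assessment table in 9.3.4 and the data collection section (11.2) also place the form at Visit 4 only. Section 8.4 adds a second route. When a woman chooses to withdraw, "we will ask if they would be willing to complete the study feedback questionnaire at the time of withdrawal". For a woman who declines only some of the procedures, "we will ask if the participant is willing to continue participating in the study and complete the rest of the study procedures" that she is prepared to do.

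**Analysis.** Section 13.4.3 states: "Acceptability of the study design and procedures will be analysed descriptively, for example by calculating mean scores derived from satisfaction scales". It continues: "We will also investigate factors associated with satisfaction, defined as a binary variable, using logistic regression". Free-text comments are also summarised, and the percentage completing the study is reported as a separate outcome.

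**Interviews.** The Process Evaluation section (9.5) states: "Up to 20 participating mothers will be asked to take part in a process evaluation at the end of the study". Consent for this is taken at entry, and interviewing continues until saturation.

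**The concern.** Women who found a procedure unacceptable are plausibly the ones most likely to leave, and the plan makes it harder to hear from them than from women who stay. A woman who stays meets the form as part of Visit 4. A woman who withdraws by choice is asked whether she is willing to fill it in. For a woman stopped by the investigator, withdrawn under 10.6.5 or lost to follow-up, no feedback request is stated.

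The analysis would not show the imbalance. No table of returns by group is planned, the regression of satisfaction names no covariates, and completion status is not mentioned as a factor. The interviews are the place to learn in depth why a procedure was disliked, but they have no sampling rule that brings in women who left or dropped a procedure.

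What is at stake is a main output of a feasibility study. A later multicentre study will use these results to decide which samples to ask for. A favourable score that mostly reflects women who stayed could carry a disliked procedure forward.

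**Working it through.** **Plan's own figure.** There is none for acceptability. The one precision statement (13.3.1, plus or minus 6% at 30% and 200 women) concerns shedding. It reproduces by rounding, 1.96 × √(0.3 × 0.7 / 200) = 6.35 points, but has no bearing here.

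**Who has a stated route to give feedback**

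| Group | Stated route |
|---|---|
| Reaches Visit 4 | Scheduled form (10.3.4.1) |
| Stops one procedure, stays in | Asked to continue (8.4), so can reach the Visit 4 form |
| Chooses to withdraw | Voluntary request at withdrawal (8.4) |
| Stopped by the investigator | None stated |
| Withdrawn under 10.6.5 | None stated |
| Lost to follow-up | GP contact and tracing only (Lost to Follow up section, also numbered 9.5); no feedback step |

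**Size under assumptions.** None of these inputs is in the documents. Let w be the share of enrolled women who leave, r the share of leavers who return a form, and p_c and p_l the satisfied shares among completers and leavers. Assume that all completers return the form.

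- True share satisfied = (1 − w) p_c + w p_l
- Observed share = [(1 − w) p_c + w r p_l] / [(1 − w) + w r]
- Bias = observed − true = (p_c − p_l) × [w − w r / (1 − w + w r)]

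Worked case: p_c = 0.90, p_l = 0.50, w = 0.20, r = 0.25. True = 0.80 × 0.90 + 0.20 × 0.50 = 0.820. Observed = (0.72 + 0.025) / (0.80 + 0.05) = 0.876. Bias = 5.6 points.

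Bias in percentage points:

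| p_l | w | True | r = 0 | r = 0.25 | r = 0.5 | r = 1 |
|---|---|---|---|---|---|---|
| 50% | 10% | 86% | 4.0 | 2.9 | 1.9 | 0 |
| 50% | 20% | 82% | 8.0 | 5.6 | 3.6 | 0 |
| 50% | 30% | 78% | 12.0 | 8.1 | 4.9 | 0 |
| 70% | 10% | 88% | 2.0 | 1.5 | 0.9 | 0 |
| 70% | 20% | 86% | 4.0 | 2.8 | 1.8 | 0 |
| 70% | 30% | 84% | 6.0 | 4.1 | 2.5 | 0 |

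The bias is proportional to p_c − p_l. It is zero if leavers are as satisfied as completers, and zero if all leavers answer.

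**Interviews.** If the 20 were a random draw from all enrolled women, the expected number of leavers would be 20w: 2 at 10% leaving, with a chance of none of 0.9^20 = 12%, and 4 at 20%, with a chance of none of 0.8^20 = 1%. The plan does not say how the 20 are chosen or whether leavers are in the pool.

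**The case against.** The plan does more for women who leave than a quick reading suggests, and several stronger inferences fail.

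- A reader might infer that women who withdrew or stopped a procedure hardly contribute. Section 8.4 does not support that. It offers the form to women who choose to withdraw, and it asks partial refusers to stay, so they can reach Visit 4. The form can also be returned by emailed link or post (10.3.4.1).
- A reader might infer that a single pooled mean is the analysis. Section 13.4.3 gives mean scores only as an example and adds regression and free text. A split by completion status is unspecified, not excluded.
- A reader might infer that the study cannot learn why women left. Section 8.4 calls for a reasonable effort to establish the reason for discontinuing.
- A reader might take the interviewees to be completers only. The text says participating mothers, consent is taken at entry, and the timing may refer to the study as a whole. The fair point is that no purposive sampling is stated.
- Completion is reported alongside acceptability, and its definition requires all three fluids and questionnaire data at all four visits. A swab that women stopped providing would lower it.

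All of this narrows the concern. What stands is that the request at withdrawal is voluntary and leaves three groups uncovered, that no returns or scores by completion status are planned, and that no interview rule includes women who left or dropped a procedure. The completion percentage shows how many women fell short, not whether a procedure was the reason. Because it disregards blood samples, it would also miss a woman who stopped only venepuncture.

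**Conclusion.** The concern holds as a risk of upward bias in a secondary outcome, not as a demonstrated bias. Under the assumed 90% satisfaction among completers, 50% among leavers and 10% to 30% leaving, it lies between 0 and 12 points, and about half that at 70% among leavers. A reader might settle on a narrower figure, such as 6 to 8 points. That needs a response of about 25% among leavers and 20% to 30% leaving, and the documents supply neither. The direction is not certain either: women withdrawn under 10.6.5 may have left for want of a freezer and been content with the procedures.

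Without response counts by group, nobody reading the results could place the study within this range. The primary endpoint is unaffected. This is a low-cost improvement to what is collected and reported.

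**What to change.** 1. **Section 8.4:** extend the feedback request to every woman who stops, for whatever reason, and can be contacted. This includes women stopped by the investigator, withdrawn under 10.6.5, or traced after loss of contact.
2. **Section 13.4.3:** report acceptability, and forms returned over forms due, separately for women who completed all procedures, women who continued in part under 8.4, and women who withdrew or were withdrawn. Identify COVID-19 withdrawals within the last group. State where a woman who stopped only blood sampling belongs, because the completion definition in 13.4.3 disregards blood samples.
3. **Section 9.5 (Process Evaluation):** keep the cap of 20, but purposively include women who withdrew or stopped a procedure, and interview them soon after they stop. Interview consent is already taken at entry.

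A mean reweighted to each group's share of enrolled women should not be added. With 20% of 200 leaving (40 women) and 25% of them answering, 10 forms would stand for 40 women. That assumes the responders resemble the non-responders, which is the point in doubt.

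The cost is protocol and SAP wording, some extra contact with women who stop, fewer completer interviews, and subgroup summaries that will be small and imprecise. The counts and denominators remain informative even so.

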9.6 Methods

10.6.1 Blood sampling

Blood samples will be taken according to the normal procedures for venepuncture in an adult by experienced staff; any suitably trained staff that could either be a member of the study team or part of the participant's routine antenatal care team will perform the blood sampling. Approximately 12mls of venous blood will be collected in 4 tubes (approximately 8ml, 1.3ml, 1.3ml and 1.3ml in respective tubes).

10.6.2 Sampling of saliva, urine and vaginal secretion

Sampling of saliva, urine and vaginal secretions will be performed by the participants themselves using the ethically approved, study specific, participant friendly written instructions on how to perform self-sampling of saliva, urine and vaginal secretions with the self-sampling kit provided.

1. Self-sampling of urine: Approximately 10ml of mid-stream urine is directly collected into a universal specimen container
2. Self-sampling of saliva: Saliva is swabbed from the oral cavity using a salivary swab in PCR transport medium
3. Self-sampling of vaginal secretions: Vaginal secretions are obtained from the low vaginal wall using a vaginal swab

10.6.2 Sample labelling and transport

For all of the study samples, the participant study identification number, date of sampling and the participant's initials will be written on the sample bottle (or tube), and time of sampling for blood samples. A pre-filled sticker will be attached to the bag containing the samples to indicate study involvement in this specific study.

All study samples will be provided to the St George's research laboratory team by the study team where the samples will be stored under the relevant St George's laboratory Standard Operating Procedures.

10.6.3 Laboratory procedures

All saliva, urine and vaginal secretion samples collected from the participants will be tested for CMV DNA via polymerase chain reaction (PCR). These tests will be performed in multiple batches and not in 'real-time' within the limitations of sample integrity. All saliva samples collected from the newborns will be tested for CMV DNA PCR in 'real-time'.

For the blood samples, CMV-specific T cell immune responses will be analysed using two commercially available IGRAs; the QuantiFERON-CMV assay and CMV-ELISPOT assay.

The blood samples that will be analysed will take into account several factors; for all participants where CMV shedding is detected, the corresponding blood samples (same participant and same visit number as when shedding was detected) and other blood samples (same participant but at different visit numbers even when shedding does not occur) will be tested. A proportion of participants where CMV shedding is not detected at all will have their blood samples tested, and will take into account the prevalence, sociodemographic details, gestational stages and the source of shedding (saliva, urine and/or vaginal secretions) of the participants that shed.

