Criteria for evaluation	
Primary outcome measure(s)
 
 • The prevalence of CMV shedding in saliva, urine and vaginal secretions of CMV seropositive women throughout pregnancy 
Secondary outcome measure(s)
 
 • The quantity of CMV shedding in saliva, urine and vaginal secretions of CMV seropositive women throughout pregnancy • The fold-differences in the prevalence and quantity of CMV shedding in saliva, urine and vaginal secretions in CMV seropositive women throughout pregnancy • The fold-differences in the prevalence and quantity of CMV

	
shedding in saliva, urine and vaginal secretions between different gestational stages of pregnancy in CMV seropositive women
 
 • The risk factors for CMV shedding in CMV seropositive pregnant women • The acceptability of the study procedures to participating pregnant women • The proportion of women approached who are recruited into the study • The proportion of participants completing the study • The relationship between cellular mediated CMV-specific immunity and CMV shedding in CMV seropositive pregnant women
	
Tertiary outcome measure(s)
 
 • The fold-differences in CMV-specific T cell immune responses, as measured by QuantiFERON-CMV and CMV-ELISPOT assays, in the evaluation of CMV-specific T cell responses with CMV shedding in CMV seropositive pregnant women
Sources of funding	Merck Investigator Studies Program
Anticipated start date:	March 2018
Anticipated primary completion date:	April 2021
Sponsor/Co-Sponsor	St George's, University of London
Key Contact names	
Sponsor contact: [name] Email: [contact] [contact]
 
Chief Investigator: [name] Email: [contact] [contact]
 
Principal Investigator: [name] Email: [contact] [contact]

Congenital cytomegalovirus (cCMV)

cCMV is the most common congenital infection in the UK. With an estimated incidence of 3 per 1000 live births (approximately 2400 cases in the UK annually) [Peckham 1983; Griffiths 1991], it is more common than many better known congenital conditions, such as Down's syndrome, spina bifida and cystic fibrosis [Dollard 2007].

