3.1 Study rationale

CMV infection is difficult to diagnose in pregnancy because it does not produce a characteristic illness. The first indication of clinical consequences of maternal infection may be seen on routine ultrasound of foetal growth, on clinical examination at birth, following abnormal hearing tests in infancy, or when older children present with hearing loss or unexplained developmental delay. This means that the opportunities to diagnose, treat and potentially improve the outcome of infection, whether by treating in pregnancy or by treating an affected infant in a timely way, are currently very limited.

Prevention of cCMV in babies born to mothers who are seropositive, or at least measures to ameliorate its consequences, is therefore a high priority.

A better understanding of the characteristics, natural history and factors associated with CMV shedding in seropositive pregnant women will help define the risk factors for horizontal as well as vertical transmission, and could provide insight into sources and routes of virus acquisition in maternal populations. Collecting samples during pregnancy to detect shedding may not only be a means of diagnosing CMV infection in a timely and convenient way, but it may also be essential for developing prevention strategies.

CMV shedding may be a suitable proxy (surrogate) for cCMV infection. If this is shown, then detection of shedding might be used as a convenient (and much more common) endpoint for trials of prevention or treatment strategies.

Additionally, measurement of CMV-specific T cell immunity may be a suitable surrogate for either CMV shedding or cCMV, or both.

If CMV virus reactivation (as a cause of shedding and / or as a cause of cCMV) is dependent on the pre-existing levels of CMV-specific T cell immunity, it is likely that altered levels can be detected earlier in CMV seropositive women in whom reactivation is going to occur. Thus, CMV-specific T cell responses may be predictive of CMV reactivation, as evident by shedding and / or vertical transmission (and cCMV). As immunomodulation is expected in pregnancy, and may vary over the course of pregnancy, longitudinal measurement of T cell immunity may provide valuable insight into the changes in immune function as pregnancy proceeds.

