14.2.3 Tertiary endpoints

- Detection and quantity of IFN- γ (IU/ml) in the plasma measured by CMV-QuantiFERON ELISA at a study visit when CMV shedding occurs in the subject
- Detection and quantity of IFN- γ (IU/ml) in the plasma measured by CMV-QuantiFERON ELISA at a study visit when CMV shedding does not occur in the subject
- Detection and quantity of IFN- γ (IU/ml) in the plasma measured by ELISPOT-CMV assay at a study visit when CMV shedding occurs in the subject
- Detection and quantity of IFN- γ (IU/ml) in the plasma measured by ELISPOT-CMV assay at a study visit when CMV shedding does not occur in the subject

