13.4.4 Tertiary endpoint analysis

For each visit, the percentage of women with a positive result from each IGRA will be estimated with 95% CIs, separately amongst participating women with and without CMV shedding. The distribution of CMV-specific T cell immune responses as measured by each IGRA will also be plotted for each of these groups.

Agreement between the categorical results from the two IGRAs will be assessed using the kappa statistic.

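### Blood is tested for all ever-shedders but only an unstated share of never-shedders, so a visit-level non-shedding IGRA percentage can depend on that share

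*Combined protocol and SAP*

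**What the plan says.** Section 10.6.3 (Laboratory procedures) decides which blood goes to the two IGRAs. For any woman with detected shedding, blood from the shedding visit is tested, and so are "other blood samples (same participant but at different visit numbers even when shedding does not occur) will be tested". For women who never shed, "A proportion of participants where CMV shedding is not detected at all will have their blood samples tested", and that choice "will take into account the prevalence, sociodemographic details, gestational stages and the source of shedding" of the women who shed. No fraction, ratio, matching rule or random draw is given.

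Section 13.4.4 (Tertiary endpoint analysis) plans IGRA positivity visit by visit with confidence intervals, and its grouping is given only by the phrase "separately amongst participating women with and without CMV shedding". It does not mention weights or the selective testing, and it does not say whether a woman without shedding is one not shedding at that visit or one who never sheds. The tertiary endpoints in section 14.2.3 are worded by visit, for example "at a study visit when CMV shedding does not occur in the subject". Section 4.2 lists the relationship between cellular immunity and shedding as a secondary objective.

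Blood sampling is optional (section 9.2), and none could be taken during the COVID-19 suspension (section 10.6.5). The rule therefore covers available blood only.

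**The concern.** If groups are set at the visit, the non-shedding group pools two kinds of women tested at different rates: ever-shedders on a negative visit, all tested where blood exists, and never-shedders, tested at an unknown rate. A simple percentage over that pool describes the tested mixture, not the cohort's non-shedding visits. It changes with a laboratory decision that the plan neither fixes nor asks anyone to record.

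This matters only if positivity differs between the two kinds. Section 3.1 gives a conditional reason to think it might: if reactivation depends on pre-existing T cell immunity, "it is likely that altered levels can be detected earlier in CMV seropositive women in whom reactivation is going to occur". Those women, sampled before they shed, are among the over-represented observations. At stake is the description of how immunity relates to shedding, a secondary objective, together with the tertiary endpoints.

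**Working it through.** **The plan's own figure.** Section 13.3.1 uses N = 200 and 30% ever-shedding. The half-width is 1.96 × √(0.3 × 0.7/200) = 6.35 points, which rounds to the stated ±6. The plan gives no precision for the IGRA analysis.

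**Inputs from the documents.** N = 200. Ever-shedding is 30%, so 60 ever-shedders and 140 never-shedders. Section 13.3.1 also cites 58% for mothers living with or caring daily for young children, and every participant lives with a child under four.

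**Assumed inputs.** Blood is available from everyone; three independent pregnancy visits; 60 or 30 never-shedders tested; IGRA positivity of 70% at ever-shedders' negative visits and 90% in never-shedders.

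**Formula.** Let A be the ever-shedders negative at a visit, m the never-shedders tested, and a and b the positivity in each. The non-shedding percentage is (A·a + m·b)/(A + m). It is free of m only if a = b.

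**At 30% ever-shedding.** Per-visit shedding is p = 1 − 0.7^(1/3) = 0.112, so 22.4 women shed at a visit and A = 60 − 22.4 = 37.6.

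| Never-shedders tested | Ever-shedders' share of group | Percentage positive | Shift |
|---|---|---|---|
| All 140 | 37.6/177.6 = 21.2% | (26.32 + 126)/177.6 = 85.8 | – |
| 60 | 37.6/97.6 = 38.5% | (26.32 + 54)/97.6 = 82.3 | 3.5 |
| 30 | 37.6/67.6 = 55.6% | (26.32 + 27)/67.6 = 78.9 | 6.9 |

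The 95% half-widths as tested are 1.96 × √(0.823 × 0.177/97.6) = 7.6 points and 1.96 × √(0.789 × 0.211/67.6) = 9.7 points. Both shifts lie inside them.

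**At 58% ever-shedding.** There are 116 ever-shedders and 84 never-shedders. p = 1 − 0.42^(1/3) = 0.251, so 50.2 shed and A = 65.8. The percentage is 81.2 with all 84 tested, 79.5 with 60 and 76.3 with 30. From unrounded values the shifts are 1.7 and 5.0.

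**Other assumptions, at 30% (60; 30 tested).**
- Positivity 80% versus 90%: 1.7; 3.4. Equal positivity: 0.
- Persistent shedding (45 of 60 shed at each visit, A = 15): 88.1 becomes 86.0 or 83.3, a shift of 2.1; 4.7.
- Reversed difference, 95% versus 90%: 91.1 rises to 91.9 or 92.8.

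**If only visits before first shedding are at 70%.** With three visits, the full shift applies at Visit 1. At Visit 2 the fraction of negative ever-shedders who have not yet shed is (1 − p)/(2 − p) = 0.470, so the shift is 0.470 × 3.5 = 1.6 or 0.470 × 6.9 = 3.2. At Visit 3 it is zero, but only if Visit 4 shedding does not count. Section 10.6.3 does not limit shedding to pregnancy. Counting Visit 4 at the same p gives 75.7 ever-shedders, A = 53.3 and a full shift of 3.4; 6.8. The not-yet-shed fractions are 33.4/53.3 = 0.626 at Visit 2 and 15.7/53.3 = 0.295 at Visit 3, giving 2.1; 4.3 and 1.0; 2.0.

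**Direction of the gap to shedding visits.** If shedding visits are also at 70%, the gap shrinks from 15.8 to 12.3 or 8.9. If they are at 95%, it widens from 9.2 to 12.7 or 16.1.

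**Check of weighting.** Under random selection, weighting each of 60 tested never-shedders by 140/60 gives (26.32 + 126)/177.6 = 85.8, the full-cohort value.

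**The case against.** The strongest reply is that the plan may not intend this grouping. Section 13.4.4 speaks of women with and without shedding, and section 10.6.3 also classifies participants. On an ever-versus-never reading the mixing disappears. That stands: section 14.2.3 favours the visit level but does not settle it. What then remains is an undefined selection of never-shedders.

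Second, selective testing is sensible, and choosing comparators by the shedders' characteristics is a legitimate design for studying a relationship. That also stands. A random draw with weights is one acceptable route, not the only one.

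Third, the analysis is descriptive, no formal contrast is planned, and the illustrated shifts at 30% ever-shedding lie within one visit's sampling error. This limits the importance. The shift is nevertheless systematic, and without a recorded fraction a reader could not correct it.

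A reader might infer several stronger things that the documents do not support:
- That the plan specifies an unweighted analysis. It is silent on weights.
- That section 3.1 predicts a difference. It states a hypothesis that begins with an if, and it does not address negative visits after shedding.
- That the synopsis line "The fold-differences in CMV-specific T cell immune responses, as measured by QuantiFERON-CMV and CMV-ELISPOT assays" commits the study to a shedding contrast. That line mentions shedding, but the tertiary objective in section 4.3 compares the two assays. The clear support for a shedding comparison is the secondary objective in section 4.2.
- That the immunity–shedding gap will be understated. It can move either way.

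**Conclusion.** The point holds on the visit-level reading. The stated testing rule and the stated grouping together can give a non-shedding percentage that does not describe the cohort, and the amount depends on an unstated fraction. The dependence itself is algebra; its size is not known. The illustrated 3.5 or 6.9 points at 30% ever-shedding, and 1.7 or 5.0 at 58%, rest on assumed positivity, assumed numbers tested, independent visits and complete blood sampling. The shift is zero if positivity is equal.

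The primary endpoint and positivity at shedding visits are unaffected. This is a minor point for a secondary objective and the tertiary endpoints, worth correcting because the correction is cheap.

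**What to change.** **Section 13.4.4.** Define the groups by shedding at the visit, and report IGRA results separately for (1) shedding visits, (2) ever-shedders' non-shedding visits and (3) never-shedders. This removes the mixing without weights and bears directly on the hypothesis in section 3.1.

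**Section 10.6.3.** State how never-shedders are selected, and record the fraction tested.

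**If a combined non-shedding percentage is wanted.** Where selection is random, overall or within strata, weight never-shedders by the inverse of the fraction tested. Where they are matched to shedders, do not combine the groups, and state that the comparison is conditional on the matching factors. Also report how many women in each group had no blood at each visit, since neither step corrects for that.

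**Cost.** No extra assays are needed. The separate groups are small: under the 30% illustration, at 70% positivity, the half-width is 1.96 × √(0.7 × 0.3/22.4), about ±19 points, for 22 shedding women, and about ±15 for 38 negative ever-shedders. For never-shedders at 90% it is about ±8 with 60 tested or ±11 with 30. Weighting can narrow or widen the combined interval. With 60; 30 tested, the weighted half-widths are 6.7; 9.0 points against 7.6; 9.7 without weights at 70% versus 90%, but 6.3; 8.7 against 6.0; 7.2 if both are 90%. The gain is a clear interpretation, not better precision.
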